4.2 Number of subjects

Approximately 60 subjects, of which at least 20 males, will be enrolled at 2-3 study sites in South America and Europe. The duration of the enrolment period is expected to be around 12 weeks.

Duration of subject participation 4.3

The total duration of the study is expected to last approximately 24 weeks (6 months), or until 60 subjects have been successfully treated. A subject will be involved in the study for 9 – 12

End of study is when enrolment has reached the target number of subjects and all subjects have completed the last study visit.

4.4 Randomization and blinding

4.4.1 Randomization

Approximately 60 subjects will be randomized in a ratio to either down-up or top-down treatment approaches. Before starting the study, a computer generated randomization list will be prepared under the supervision of a designated statistician from the Sponsor. The randomization list will be stratified by site and gender. Randomization numbers will be allocated in ascending sequential order within each strata. Randomization will be performed

using an Interactive Response System by assigning each subject to the two treatment groups according to the randomization list.

4.4.2 Blinding

The IPR will review blinded pairs of photographs from pre and post treatment. No information regarding treatment group or visit will be available to the photographic reviewer. The photographs will be coded and a separate key, not available to the IPR, will be used to pair the IPR evaluations to the correct subject and visit.

4.4.3 Emergency unblinding

Not applicable as the treating Investigator is not blinded to treatment.

4.5 Medical history

History of relevant surgical events and medical conditions should be documented (including any prior dermatological procedures or implants) in the electronic case report forms (eCRF) using medical terminology.

4.6 Prior and concomitant therapies

Except as noted below, concomitant medications or other treatments or procedures may be utilised when the PI or his/her authorised designee considers it medically necessary. Information regarding any use of concomitant medications, including over-the-counter medications administered during the study are to be recorded in the eCRF. The generic name or the trade name of all concomitant medication or a description of the procedure and the reason for its use shall be documented in the eCRF.

The following medications, treatments, and procedures are restricted or prohibited during the study:

- Use of concomitant medication that have the potential to prolong bleeding times such
 as anticoagulants or inhibitors of platelet aggregation (e.g. aspirin [except low dose
 aspirin] or other non-steroidal anti-inflammatory drugs [NSAIDs], Omega 3 or
 Vitamin E), within 14 days prior to injection. Omega 3 and Vitamin E are acceptable
 only as part of a standard multivitamin formulation.
- Treatment with chemotherapy, immunosuppressive agents, immunomodulatory therapy (e.g. monoclonal antibodies,); systemic corticosteroids (inhaled corticosteroids are allowed) within 3 months prior to injection visits (visit 2, 3 and 4).
- Lidocaine should be used with caution in subjects receiving other local anaesthetics
 or agents structurally related to amide-type anaesthetics, e.g. certain antiarrhythmics,
 as the systemic toxic effects can be additive.
- Procedures involving an active dermal response in the facial area including the lips
 (e.g. tissue augmenting therapy, contouring or revitalisation treatment with permanent
 or non-permanent fillers, mesotherapy, fat-injection, neurotoxin (below the level of the
 horizontal line from the lower orbital rim), laser or light treatment, chemical peeling or
 dermabrasion) are prohibited.
- Facial surgery including liposuction, insertion of permanent implants in the facial area, planned sinus surgery or dental root surgery, or tattoo in the treatment area are prohibited.

Use of topical facial corticosteroids or prescription retinoids or systemic retinoid treatment near or in the treatment area are prohibited.

Participation in any other clinical study is prohibited.

If a subject receives prohibited therapy during the study, a protocol deviation should be documented. The subject shall continue in the study for the scheduled follow-up visits unless otherwise instructed by the Sponsor.

4.6.1 Recording

Prior and concomitant therapies are to be recorded in the eCRF and reviewed, and updated if needed, at each visit.

Any new concomitant therapy or modification of an existing therapy may be linked to an AE. A corresponding AE form must be completed to account for the change in therapy, except in some cases such as therapy used for prophylaxis, dose modification for a chronic condition.

Doc id 05DF1910 Clinical Study Protocol ♣ GALDERMA MA-42248

Schedule of Events

Table 1. Schedule of events

	Visit 1	Visit 2	Visit 3	Visit 4	Visit 5
	Screening ¹	Baseline/ Day 1	Week 3	Week 6	Week 9
		(within 3 weeks after screening)	(21 ± 3 days from visit 2)	(42 ± 3 days from visit 2)	(63 ± 5 days from visit 2)
Informed Consent	X	(X) ²			
Demographic Data including, Fitzpatrick skin type, medical history & concurrent diseases, previous facial treatments/procedures	X	(X) ²			
Weight and height	X	(X) ²			X^3
Inclusion /Exclusion Criteria	X	X			
Concomitant Medication/ Procedures	X	X	X	X	X
Urine Pregnancy Test		X	X	X ⁴	
Photography 2D		X	X	X	X
Randomization		X			
Treatment ⁵		X	X	X ⁶	
Adverse Events ⁷		X	X	X	X
Investigator Assessment					
GAIS			X	X	X
Naturalness CCI around the chin.		X ⁸	X ⁸	X	X
Subject Assessment					

- The screening visit and baseline visit (visit 2) may be performed on the same day
- Screening visit assessments should be performed on the same day as the baseline visit if no separate screening visit has been 2) completed
- 3) Weight only
- If touch-up treatment is planned 4)
- Treatment to be performed after all assessments have been completed. 5)
- Optional touch-up injection
- AE reporting period starts at the baseline visit after randomization 7)
- Only applicable questions 8)
- 9)
- essments to be performed after end of study 10)
- 11)

4.8 Visits

4.8.1 Visit 1: Screening Visit

The screening visit and baseline visit (visit 2) may be performed on the same day. The following activities and screening assessments will be performed within three weeks prior to baseline.

- Informed Consent
- Demographic Data including, Fitzpatrick skin type, medical history & concurrent diseases, previous facial treatments/procedures, see section 4.9.
- Weight and height
- Inclusion /Exclusion Criteria
- Concomitant Medication/ Procedures

4.8.2 Visit 2: Baseline Visit (First Injection)

Include screening visit assessments if screening and baseline is performed on the same day.

- Inclusion / Exclusion Criteria
- Concomitant Medication/ Procedures
- Urine Pregnancy Test
- Photography 2D
- Randomization
- Treatment (to be performed after efficacy assessments)
- Adverse Events

Investigator assessments

Subject assessments

- Subject satisfaction questionnaire (only applicable questions)

4.8.3 Visit 3: 3-Week Visit (Second Injection)

- Concomitant Medication/ Procedures
- Urine Pregnancy Test
- Photography 2D
- Treatment (to be performed after efficacy assessments)
- Adverse Events

Investigator assessments

GAIS

Naturalness/CCI (only applicable questions)

CCI

Subject assessments

· Subject satisfaction Questionnaire

4.8.4 Visit 4: 6-Week Visit (Optional Touch-up)

- Concomitant Medication/ Procedures
- Urine Pregnancy Test (if touch-up treatment is planned)
- Photography 2D
- Touch-up treatment (to be performed after efficacy assessments)
- Adverse Events

Investigator assessment

- GAIS
- Naturalness/CCI around the chin/improvement in the submental area
- CCI

Subject assessment

· Subject satisfaction Questionnaire

4.8.5 Visit 5: 9-Week Visit (End of Study)

- Weight
- · Concomitant Medication/ Procedures
- Photography 2D
- Adverse Events

Investigator assessments

- GAIS
- Naturalness/
- CCI

Subject assessments

· Subject satisfaction Questionnaire

4.9 Demographics and baseline assessments

- Date of birth
- Gender
- · Child bearing potential
- Race and ethnic origin
 - Ethnicity: Hispanic or Latino, Not Hispanic or Latino
 - Race: American Indian/Alaskan Native, Asian, Black, Native Hawaiian or other Pacific Islander, White, other
- Fitzpatrick skin type (FST), see Table 2 below.

Table 2. Fitzpatrick Skin Types (FST)*

Skin type	Skin color	Skin characteristics
I	White; very fair; red or blond hair, blue eyes; freckles	Always burns, never tans
II	White; fair; red or blond hair; blue, hazel or green eyes	Usually burns, tans with difficulty
III	Cream white; fair with any eye or hair color; very common	Sometimes mild burn, gradually tans
IV	Brown; typical Mediterranean Caucasian skin	Rarely burns, tans with ease
V	Dark brown; Middle Eastern skin types	Very rarely burns, tans very easily
VI	Black	Never burns, tans very easily

FST is a skin classification system that categorizes different skin colors, and their reactions to ultraviolet light.†

^{*} https://www.verywell.com/fitzpatrick-classification-scale-1069226

[†] Fitzpatrick T.B. (1988). The validity and practicality of sun-reactive skin types I through VI. Arch. Dermatol. 124, 869–871.

05DF1910 Clinical Study Protocol 👶 GALDERMA MA-42248

Subjects

5.1 Subject information and informed consent

The PI or his/her authorized designee must always use the IEC-approved subject information and informed consent form (ICF) and it must not be changed without prior discussion with the Sponsor and approval from the applicable IEC.

It is the responsibility of the PI or his/her authorized designee to give each subject prior to inclusion in the study, full and adequate verbal and written information regarding all aspects of the clinical study that are relevant to the subject's decision to participate throughout the study, e.g. explain the purpose and procedures of the study, the duration and number of expected participants, possible risks involved, and the opinion of the IEC. The subject shall be informed that the participation is confidential and voluntary and that the subject has the right to withdraw from the study at any time, without any consequences to his/her future medical care, treatment or benefits to which the subject is otherwise entitled. The information shall be provided in a language clearly and fully understandable to the subject. The subject shall be given sufficient time to read and understand the ICF and to consider participation in the study. Before any study-related activities are performed, the ICF shall be personally signed and dated by the subject and the PI or delegated Investigator. The consent includes information that data will be collected, recorded, processed, and may be transferred to both EU and non-EU countries. The data will not contain any information that can be used to identify any subject.

Photographs collected during the study will be analysed and stored in a database by the Sponsor and its representatives in order to evaluate the effect of the treatment in the study. The subjects will be recognizable on the photographs, but their names will not be disclosed.

All signed ICFs shall be filed in the Investigator file. The subject shall be provided with a copy of the signed and dated ICF and any other written information.

The Investigator shall ensure that important new information is provided to new and existing subjects throughout the study.

5.2 Inclusion criteria

The subjects must meet the following criteria to be eligible for the study:

- 1. Subjects willing to comply with the requirements of the study and providing a signed written informed consent.
- Subjects willing to undergo augmentation and correction therapy in the studied indications
- Subjects willing to abstain from any other facial plastic surgical or cosmetic procedures for the duration of the study (e.g., laser or chemical resurfacing, facelift,
- Adult males or non-pregnant, non-breastfeeding females and women of non-child bearing potential over the age of 21.
 - Urinary pregnancy test must be negative for females of childbearing potential at screening and all injection visits.

05DF1910 Clinical Study Protocol 👶 GALDERMA MA-42248

> Definition of non-child bearing potential: Women of non-childbearing potential are defined as those who have no uterus, ligation of the fallopian tubes, or permanent cessation of ovarian function due to ovarian failure or surgical removal of the ovaries. Postmenopausal women must be amenorrheic for at least 12 months to be considered of non-childbearing potential.

5. If the subject is a female of childbearing potential, she agrees to use an acceptable form of effective birth control for the duration of the study and is willing to take a urine pregnancy test at the screening/enrolment visit and prior to treatment.

Acceptable forms of effective birth control include:

- Barrier methods of contraception: Condom or Occlusive cap (diaphragm or cervical caps) with spermicidal foam/gel/film/cream/suppository;
- Bilateral tubal ligation;
- Combined oral contraceptives (estrogens and progesterone), implanted or injectable contraceptives on a stable dose for at least 28 days prior to Day 1;
- Hormonal or copper intra uterine device (IUD) inserted at least 28 days prior to Day 1;
- Vasectomized partner for at least 3 months prior to screening;
- Strict abstinence (at least one month prior to baseline and agrees to continue for the duration of the study or use acceptable form of birth control).

5.3 **Exclusion criteria**

The presence of any of the following exclusion criteria will exclude a subject from enrolment in the study:

- Known/previous allergy or hypersensitivity to any injectable HA gel or to gram-1. positive bacterial proteins.
- 2. History of allergy or hypersensitivity to lidocaine or other amide-type anaesthetics, or topical anaesthetics or nerve blocking agents (if such products are intended to be used for that subject).
- 3. Previous or present multiple allergies or severe allergies, such as manifested by anaphylaxis or angioedema, or family history of these conditions.
- 4. Previous use of any permanent (non-biodegradable) treatment, lifting threads, permanent implants or autologous fat below the level of the horizontal line from the lower orbital rim.
- 5. Previous use of any semi-permanent treatment (e.g., calcium hydroxylapatite or Poly-L-Lactic acid) below the level of the horizontal line from the lower orbital rim within 24 months of the baseline visit.
- Previous use of any HA based or collagen based biodegradable facial tissue augmentation therapy below the level of the horizontal line from the lower orbital rim within 12 months of the baseline visit.
- 7. History of other facial treatment/procedure in the previous 6 months that in the Treating Investigator's opinion, would interfere with the study injections and/or study assessments or exposes the subject to undue risk by study participation, e.g.:

Doe id 05DF1910 Clinical Study Protocol GALDERMA MA-42248

- Resurfacing (laser, photo modulation, intense pulsed light [IPL] radio frequency, dermabrasion, needling, chemical peel or other ablative/nonablative procedures (such as ultrasound and cryotherapy))
- Mesotherapy
- Lipolytic injections (e.g. deoxycholic acid or other lipolytic substances)
- Botulinum toxin injections below the level of the horizontal line from the lower orbital rim
- 8. Previous facial surgery, within 12 months, below the level of the horizontal line from the lower orbital rim.
- History of cancer or previous radiation near or on the area to be treated.
- Presence of any disease or lesions near or on the area to be treated, e.g.:
 - Inflammation, active or chronic infection (e.g., in mouth, head and neck region)
 - Perioral dermatitis, active herpes simplex or herpes zoster lesions, or outbreak within 4 weeks from baseline, or history of four outbreaks, or more, during the last year
 - Scars or deformities
 - Cancer, or precancer such as actinic keratosis or actinic cheilitis
- 11. Presence of tattoo, piercing, beard or facial hair, which, in the Treating Investigator's opinion, would interfere with the study injections and/or study assessment.
- 12. Presence of a dental, oral, or facial condition which, in the Treating Investigator's opinion, would interfere with the study injections and/or study assessment, e.g. has dentures or any device covering all or part of the upper palate, and/or severe malocclusion or dentofacial or maxillofacial deformities.
- 13. An underlying known disease, a surgical or medical condition that would expose the subject to undue risk, e.g. active hepatitis, autoimmune disease, history of bleeding disorders, connective tissue diseases such as rheumatoid arthritis, systemic lupus erythematosus, polymyositis, dermatomyositis, or scleroderma.
- 14. Use of concomitant medication that have the potential to prolong bleeding times such as anticoagulants or inhibitors of platelet aggregation (e.g. aspirin [except low dose aspirin] or other NSAIDs, Omega 3 or Vitamin E), within 14 days prior to injection. Omega 3 and Vitamin E are acceptable only as part of a standard multivitamin formulation.
- 15. Treatment with chemotherapy, immunosuppressive agents, immunomodulatory therapy (e.g. monoclonal antibodies,), systemic corticosteriods (inhaled corticosteroids are allowed) within 3 months prior to Baseline visit.
- 16. Use of topical facial corticosteroids or prescription retinoids (below the level of the horizontal line from the lower orbital rim) within 1 month of the Baseline visit or systemic retinoid treatment within 6 months of the Baseline visit.
- 17. Presence of any condition, which in the opinion of the Treating Investigator makes the subject unable to complete the study per protocol, e.g.

GALDERMA

Title
05DF1910 Clinical Study Protocol

MA-42248

- Subjects not likely to avoid other prohibited facial cosmetic treatments
- Subjects not likely to complete the study because of other commitments
- Subjects anticipated to be unavailable for visits, incapable of understanding the investigational assessments or having unrealistic expectations of treatment result
- Subjects who have a concomitant condition (e.g. acute viral or bacterial infection with fever) that might confuse or confound study treatments or assessments
- Participation in any interventional clinical study within 30 days of screening.
- Study site personnel, close relatives of the study site personnel (e.g., parents, children, siblings, or spouse), employees, or close relatives of employees at the Sponsor Company.

5.4 Subject number

Each subject who has signed the ICF will be assigned a subject number The subject numbers will be allocated in ascending order within each centre. The reason for excluding a consenting subject from entering the study should be specified in each case. A screen failure should not be re-entered in the study.

For the duration of the clinical study, each subject will be identified using the subject number for all documentation and discussion.

5.5 Withdrawal of subjects

An investigator may decide to discontinue a subject from the clinical study for safety reasons.

Although the importance of completing the entire clinical study should be explained to the subject by the clinical study personnel, any subject is free to discontinue participation in this clinical study at any time and for whatever reason, specified or unspecified, and without any prejudice. No constraints are to be imposed on the subject, and when appropriate, a subject may be treated with other conventional therapy when clinically indicated.

When a subject does not complete the clinical study, he/she will be fully assessed, if such assessment is possible. The procedures designated for the early termination visit should be completed for all subjects discontinuing the clinical study and the appropriate eCRF should be completed.

All discontinuations and the reason for discontinuation are to be documented by the investigator on the Exit form.

For discontinuation due to and AE, the Adverse Event form is to be completed. The investigator should also ensure that the subject receives suitable therapy for the AE.

A subject who has been randomized and assigned a kit number/randomization number cannot be replaced by another subject if he/she discontinues the clinical study for any reason. Additional subjects could be enrolled (randomized/assigned to treatment) in order to attain the number of evaluable subjects.

Pregnancies occurring during the screening period are considered as screening failures; they should be recorded as such in the eCRF and no pregnancy form is to be completed.

In case of a pregnancy occurring after the baseline visit, follow the procedures described in section 8.1.8. The subject may remain in the study, but no invasive procedure should be conducted.

The Sponsor may also decide to prematurely terminate or suspend a subject's participation in the clinical study.

Potential reasons for discontinuation are defined below:

The withdrawal criteria are:

- Medical reasons: If the subject suffers from a medical condition that in the judgement
 of the Investigator makes it medically necessary to withdraw the subject. The specific
 rationale for Investigator-initiated withdrawal of a subject for medical reasons shall
 document the specific condition for withdrawing the subject.
- Safety reasons: If a subject suffers an AE, which in the judgment of the Investigator or the Sponsor presents an unacceptable consequence or risk to the subject.
- Withdrawal of informed consent: A subject can withdraw their consent to participate
 in the study at their own request or be withdrawn from participation in the study at the
 request of their legally authorised representative at any time for any reason.
- Lost to follow-up: If a subject does not return for a scheduled visit, reasonable effort shall be made to contact that subject, e.g. call three times at different hours and leave messages if applicable before declaring the subject lost to follow-up.
- Other: Examples of other reasons for withdrawal may be failure to comply with protocol requirements or to complete the protocol-specified evaluations.

If reason for discontinuation is "withdrawal by subject" or "other", the subject will be questioned to rule out the possibility of an AE. If the AE led to discontinuation then "adverse event" should be chosen as the reason for discontinuation, rather than "withdrawal by subject" or "other".

If an AE which, according to the Investigator's assessment, is related to the use of any of the study products and is still ongoing at the time of the withdrawal, the Investigator shall follow-up the subject until the AE resolves, is assessed by the Investigator to be "chronic" or "stable" or for at least 3 months.

Subjects who have received prohibited concomitant medications or therapies should be followed according to protocol.

6. Study Products

The term "study product" refers to Restylane Defyne.

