8.1.8 Pregnancy

Pregnancy itself is not regarded as an AE.

If there is a pregnancy during the study period the subject must be withdrawn from any following study treatment, but should continue to be followed within the study and the outcome of pregnancy must be reported even if the delivery occurs after study completion.

A pregnancy confirmed during the study period must be reported by the Investigator on a pregnancy report form immediately upon acknowledge be submitted to the Sponsor according to contact details specified in section 8.1.5. The report can be prospective or retrospective. Follow-up shall be conducted to obtain outcome information on all prospective reports.

Cases that led to fetal distress, fetal death or a congenital abnormality or birth defect are to be regarded as SAEs and shall be reported on the exposure in utero report form to the Sponsor immediately but no later than 24 hours after the Investigators awareness. These events shall be handled as SAEs during data processing. Other complications during the pregnancy that are related to the pregnant woman and fulfils any serious criteria, such as pre-eclampsia

Print date:

requiring hospitalization, shall be reported and handled as SAEs. Elective abortions without complications shall not be reported as AEs.

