10.5 Handling of missing data

Study data will be presented based on observed cases, i.e. no imputation of missing values will be performed.

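### Section 5.5 permits study withdrawal for non-compliance or missed evaluations, so week-6 and week-9 outcomes of fully treated subjects can be lost from an observed-case analysis

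*Combined protocol and SAP*

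**What the plan says.** Section 5.5 describes withdrawal at the level of the study. For safety it states: "An investigator may decide to discontinue a subject from the clinical study for safety reasons". Its list of potential reasons covers medical reasons, safety reasons, withdrawal of consent, loss to follow-up and a residual category, of which it says: "Examples of other reasons for withdrawal may be failure to comply with protocol requirements or to complete the protocol-specified evaluations".

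Other text keeps subjects under observation when treatment or conduct departs from plan:

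- On prohibited therapy, section 4.6 says: "The subject shall continue in the study for the scheduled follow-up visits unless otherwise instructed by the Sponsor". Section 5.5 agrees: "Subjects who have received prohibited concomitant medications or therapies should be followed according to protocol".
- On pregnancy, section 8.1.8 says the subject "must be withdrawn from any following study treatment, but should continue to be followed within the study". Section 5.5 says only that such a subject may remain.

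For those who do leave, section 5.5 asks for a full assessment where possible and adds: "The procedures designated for the early termination visit should be completed for all subjects discontinuing the clinical study". Table 1 and sections 4.8.1 to 4.8.5 list no such visit.

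On analysis, section 10.5 says: "Study data will be presented based on observed cases, i.e. no imputation of missing values will be performed". Section 10.1 bases all efficacy analyses on the MITT set, which it explains as subjects treated at both baseline and week 3.

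**The concern.** The residual category treats a departure from protocol, or an evaluation not completed, as a possible ground for ending a subject's participation. Neither is a reason to stop looking at the outcome. A subject who has had both treatment sessions is in the efficacy set. If that subject leaves before week 6 or week 9, the remaining GAIS, naturalness and satisfaction ratings are never made, and the observed-case rule drops the subject from those denominators.

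Two features make this more than housekeeping. First, the treating Investigator knows the group (4.4.3), can discontinue subjects (5.5), and also rates GAIS and naturalness (7.3, Appendix 5). Second, the rationale in 2.3 is to learn whether the order of treatment affects the endpoints and to inform later treatment guidance. Uneven loss between the down-up and top-down groups would bear on that question. The option in 5.5 to enrol additional subjects restores the number of evaluable subjects but not the missing outcomes.

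**Working it through.** **1. Where the route operates.** The plan has no sample-size calculation to reproduce: 10.8 gives about 60 subjects, 30 per group (2 × 30 = 60), and says this is not statistically based. The route depends on when the subject leaves.

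- *Before the week-3 injection.* The MITT definition in 10.1 already removes the subject from efficacy. Further follow-up would add safety data only, unless that set also changed.
- *After the week-3 injection.* The subject is in MITT, taking treatment at both visits as the operative definition. Leaving before week 6 loses the week-6 and week-9 results; leaving between weeks 6 and 9 loses week 9. Here 5.5 has its effect.

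**2. What the exit assessment recovers.** Section 5.5 refers to designated early termination procedures, but none are listed, and no rule says whether data from that visit count as week 6, week 9 or neither. As written, it cannot be relied on to fill the gap.

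**3. Size, by illustration.** Inputs: n = 30 per group (10.8). Assumed: 25 improved if all were followed to week 9, and 1 to 4 subjects lost. The protocol gives neither an outcome rate nor a withdrawal rate.

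Observed-case proportion = (25 − improvers lost) / (30 − all lost). With no loss, 25/30 = 83.3%.

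| Lost | All non-improvers | Change (points) | All improvers | Change (points) |
|---|---|---|---|---|
| 1 | 25/29 = 86.2% | +2.9 | 24/29 = 82.8% | −0.6 |
| 2 | 25/28 = 89.3% | +6.0 | 23/28 = 82.1% | −1.2 |
| 3 | 25/27 = 92.6% | +9.3 | 22/27 = 81.5% | −1.9 |
| 4 | 25/26 = 96.2% | +12.8 | 21/26 = 80.8% | −2.6 |

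Other assumed rates behave alike. With 24/30 (80%) and three lost, the range is 21/27 = 77.8% to 24/27 = 88.9%. With 27/30 (90%) and three lost, it is 24/27 = 88.9% to 27/27 = 100%.

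These are extremes. If those lost have the same improved fraction as those who stay, the expected proportion is unchanged. If the loss occurs in one group only, the change in the table appears as a between-group difference of the same size.

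**4. How stopping is recorded.** The action-taken list for AEs in 8.1.3 includes withdrawal of the subject but no entry for a study injection stopped or not given. Apart from pregnancy, the protocol has no general status for a subject who receives no further injection and is still followed.

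**The case against.** The strongest reply is that the text is permissive and ordinary handling lies elsewhere. Section 5.5 offers examples that may be reasons. Assessments not done are indicated in the eCRF (9.2.1), and deviations are logged, reviewed and listed (12.1, 12.3.2, 10.7). The prohibited-therapy rule is specific and consistent in both places, so a general example should not override it. After week 3 the only injection left is the optional touch-up; not giving it is already within protocol, and visits 4 and 5 go ahead.

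Much of this stands. A reader might infer that one missed questionnaire must end data collection; the documents only allow withdrawal. A reader might also infer that leaving ends all observation. It does not: 5.5 requires follow-up of ongoing related AEs and an exit assessment if possible, and 8.1.7 covers related events with onset after the last visit if the Investigator learns of them. A reader might further infer that groups will lose subjects unequally because the first treated area differs. The documents give no AE rates by area, and the method for any group comparison is not readable in the public text.

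What survives is that the permission exists, fits poorly with 4.6 and 8.1.8, leaves similar cases to site discretion, and rests on an undefined visit. It also remains usable after week 3, where the efficacy results are exposed.

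**Conclusion.** The point holds as a worthwhile, inexpensive improvement. Section 5.5 permits loss of week-6 and week-9 efficacy data from subjects treated at both visits, for reasons that do not require anyone to stop observing them, and the analysis does nothing to compensate.

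The tempting stronger conclusion is that poor outcomes drop out and success rates are inflated. The documents do not establish that. An AE-related exit may go with a poor rating, but non-compliance or a missed evaluation need not. For up to four losses in an assumed group of 30 with 25 improved, the change runs from −2.6 to +12.8 points. The upper end needs four of the five non-improvers and no improvers to leave. Neither the number lost nor the direction can be fixed from the protocol.

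Subjects stopped before week 3 are outside this conclusion for efficacy; their exclusion follows from the MITT definition.

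**What to change.** Amend the protocol as follows.

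1. In 5.5, delete non-compliance and incomplete evaluations as reasons for study withdrawal. State that these subjects stay for the remaining scheduled photographs, GAIS, naturalness, satisfaction and AE assessments.
2. Reconcile 5.5 with 4.6 and 8.1.8, including the different wording on pregnancy, so that stopping injections is recorded separately from leaving the study. Add a matching entry to the action-taken list in 8.1.3.
3. State that the early termination visit consists of the visit 5 procedures in 4.8.5, add it to Table 1, and give a rule for which scheduled visit its data count toward. Make clear that it respects section 11, which bars new data once consent is withdrawn.

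Leave the medical, safety and Sponsor withdrawal criteria as they are, along with all decisions on who is injected. Restricting study exit to consent withdrawal, loss to follow-up or the subject's own wish would remove those criteria; that is a clinical matter outside this point.

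The cost is a wording amendment, one eCRF code and a mapping rule. The visits are already scheduled. The downside is a few visits for subjects no longer being treated or not fully compliant.
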